5.4 Follow-up

No follow-up will be conducted in this study.

6. STUDY DATA COLLECTION AND ASSESSMENTS

6.1 Image Acquisition Data

The following data will be collected on a study CRF during the mammography exams:

- 1) Date of mammography exam
- 2) Demographic information, including age and ethnicity
- 3) Menopausal status
- 4) Size of paddle used for imaging (per breast) – 24 x 29.8 cm or 19 x 23 cm
- 5) Breast of interest – First breast imaged or Second breast imaged
- 6) Laterality of the breast of interest – Right or Left

When a subject's mammography exam is complete, the following data will be collected on a study CRF:

- 1) Considering PAC only, did the technologist intervene while the subject was controlling the compression? Yes or No. If yes, please indicate which of the following interventions were done:
 - a. Use footswitch to increase compression
 - b. Used footswitch to decrease compression
 - c. Used manual knobs to increase compression
 - d. Used manual knobs to decrease compression
- 2) Considering PAC only, would you have repeated the image acquisition? Yes or No. If yes, please select the option below that best describes the reasoning.
 - a. Positioning
 - b. Compression
 - c. Motion
 - d. Other, please explain.
- 3) Considering the TC compression only, did you repeat image acquisition? Yes or No. If yes, please select the option below that best describes the reasoning.
 - a. Positioning
 - b. Compression
 - c. Motion
 - d. Other, please explain.
- 4) Compression force (daN) – obtained from DICOM header
- 5) Breast thickness (mm) – obtained from DICOM header
- 6) AGD (mGy) – obtained from DICOM header
- 7) Per-view acquisition parameters (mAs and kVp) – obtained from DICOM header

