Procedures/Methods:	
The study population will consist of adult asymptomatic women presenting for screening 2D mammography. One breast of each subject will be identified as the “breast of interest,” which will undergo study-specific 3D imaging consisting of two-view (craniocaudal and mediolateral oblique) PA compression and image acquisition, followed by two-view technologist-controlled (TC) compression and image acquisition. The breast of interest will be randomly assigned to either the first breast imaged during the exam or the second breast imaged. TC compression and imaging, and procedures performed on the subject’s other breast will be conducted per standard of care.
 
Following image acquisition, 3D image quality evaluation will be conducted by MQSA-qualified readers. Prior to the reading session, images will be de-identified and the following information will be removed from the DICOM header to blind readers to the compression mode used during acquisition: time stamp, compression force, and breast thickness. The image sets will also be randomized for presentation during the image attribute reviews. Two (2) readers will evaluate each PAC and TC compression image set collected from each subject’s breast of interest and assess the acceptability of image attributes, as defined in the Guidance for Industry and FDA Staff - Class II Special Controls Guidance Document: Full-Field Digital Mammography System (2012). A third reader will provide adjudication, if there is disagreement for a given image set’s overall clinical image quality.
 
Workflow data, including the incidence of technologist intervention during acquisition and need for repeat image acquisition, will also be collected.
 
The proportion of PAC image sets that are of equal or higher acceptability than TC image sets will be calculated. A 95% confidence interval will be calculated using asymptotic method with continuity correction. The proportion of image sets indicated for repeated

	
image acquisition when using PA mode or TC mode will be summarized. Other endpoint data will be summarized using descriptive statistics. No statistical hypothesis is being tested in this study.

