5.3 Description of Study Procedures

5.3.1 Image acquisitions

Each subject will undergo her regularly scheduled breast imaging exam per standard practices at the investigational site, with the exception of the study-specific image acquisitions using PAC. The site uses combo mode (2D and 3D imaging) for screening mammography, and does not decompress between 3D and 2D imaging for a given view. Additionally, 3D acquisitions are conducted first per standard of practice. Thus, the sequence of imaging procedures will be conducted for the breast of interest, as shown in Figure 4. There shall be no repeat imaging administered using PAC mode, and standard of care will be used for imaging of the subject's other breast.

[figure not shown]

Figure 4 – Sequence of imaging procedures for the breast of interest (dark boxes = PAC, study-specific imaging, white boxes = standard of care (SoC) at the site).

A minimum of three (3) site technologists will perform the image acquisitions and related study procedures. Study procedures shall not impact the order in which the left and right breasts are imaged during the subjects' exams.

There will be two (2) study-specific image sets of the breast of interest for each subject. Image sets will consist of CC and MLO views obtained using PAC and CC and MLO views obtained using TC compression.

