10.3.3 Analysis of Secondary and Exploratory Endpoints

The proportion of image sets indicated for repeated image acquisition when using PAC mode or TC mode will be summarized. This analysis will also be performed for subgroups defined by the randomized breast of interest.

The acceptability for individual mammographic attributes will be summarized by attribute.

Patient characteristics (demographics, breast thickness) and procedural characteristics (radiation dose, compression force) will be summarized using descriptive statistics. Compression force analysis will also be performed for subgroups defined by the randomized breast of interest.

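### The technologist's hypothetical repeat judgement for patient-assisted compression is due only after the comparator images of the same breast, so it may be influenced by them; recording it earlier is a minor, cheap improvement

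*Combined protocol and SAP*

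**What the plan says.** Section 6.1 (Image Acquisition Data) has two blocks of data. The first, filled in during the exam, covers the date, demographics, menopausal status, paddle size, breast of interest and laterality. The second is introduced by the wording "mammography exam is complete, the following data will be collected on a study CRF" and holds the technologist's three items:

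- Item 1, on interventions: "Considering PAC only, did the technologist intervene while the subject was controlling the compression", followed by the type of intervention.
- Item 2, on PAC repeats: "Considering PAC only, would you have repeated the image acquisition? Yes or No".
- Item 3, on TC repeats: "Considering the TC compression only, did you repeat image acquisition? Yes or No".

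The Study Synopsis (Procedures/Methods) fixes the order for the breast of interest: two-view PAC, "followed by two-view technologist-controlled (TC) compression and image acquisition". Section 5.3.1 adds: "There shall be no repeat imaging administered using PAC mode". Section 1.2 says that study staff know the compression mode.

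Section 3.2.2 makes repeat indications from the technologist, the readers or both a secondary endpoint. Section 10.3.3 summarises the proportion of image sets indicated for repeat by mode and continues: "This analysis will also be performed for subgroups defined by the randomized breast of interest". Section 4.6 randomises the breast of interest to be the first or the second breast imaged, about half the subjects each way. As a general rule, Section 11.1.1 has electronic forms filled in as the information arises.

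**The concern.** Item 2 asks for a judgement about an act that the protocol forbids, so no observed event can confirm the answer. Section 6.1 asks for it when the same breast has already been compressed and imaged under TC, by a person who knows which acquisition was which. A good TC image could make the PAC image look worse by contrast. It could also make a PAC repeat seem unnecessary, because an adequate image now exists. Either would let the comparator into the technologist part of the PAC repeat endpoint, and no analysis could take it out afterwards.

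A smaller matter concerns the breast-order subgroups. If the breast of interest is imaged first, some imaging of the other breast still has to be done before the form is due. The time between the PAC images and the judgement would then differ between the two randomised groups that Section 10.3.3 summarises separately. A difference in repeats between them could reflect subject learning, which the randomisation was meant to address, or the different delay.

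**Working it through.** The plan gives no figure for the repeat endpoint. Its only precision figure (Section 10.2) concerns the primary proportion and does not bear on this point. The check is therefore a reading of the sections together, with simple arithmetic.

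**Timing**

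1. Item 2 is due after the exam is complete (6.1).
2. TC imaging of the same breast follows PAC in every subject (Synopsis). The order of modes is not randomised; only the breast is (4.6).
3. From 1 and 2, TC imaging is always finished before item 2 is due.
4. Staff are unblinded (1.2), and none of the bias controls listed there covers this judgement.
5. The documents do not say outright that the technologist looks at the TC images before answering. Deciding whether to repeat TC for positioning, compression or motion (item 3) makes it a fair inference.

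**Weight of one answer**

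Inputs: 30 evaluable subjects (10.2) and about half in each breast-order group (4.6), so about 15.

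- Overall: 1/30 = 3.3 percentage points.
- Breast-order subgroup: 1/15 = 6.7 percentage points.

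These give the weight of a single changed answer. They do not say how often answers would change.

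**Illustration (assumed rates, not in the documents)**

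Let r be the PAC repeat rate that would be recorded without knowledge of TC, taken as 3% to 10%. Let f be the share of answers that change after TC, taken as 2% to 10%.

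- If some answers change from no to yes, the recorded rate is r + (1 − r)f. Lowest: 0.03 + 0.97 × 0.02 = 4.9%. Highest: 0.10 + 0.90 × 0.10 = 19.0%.
- If some answers change from yes to no, the recorded rate is r(1 − f). Lowest: 0.03 × 0.90 = 2.7%. Highest: 0.10 × 0.98 = 9.8%.

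The documents do not say which case applies, if either.

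**Views between the last PAC view and the form**

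Figures 2 and 4 are not shown, so two sequences are taken as assumptions, with two views per breast.

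| Assumed sequence | Breast of interest first | Breast of interest second |
|---|---|---|
| One breast finished before the other | 2 TC + 2 other breast = 4 | 2 TC = 2 |
| Views alternate between breasts, PAC and TC paired within a view | 1 TC + 1 other breast = 2 | 1 TC = 1 |

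Under both, the gap is longer in the first-breast group. Its size is not fixed.

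**What is not touched**

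- Item 1 records whether the footswitch or knobs were used. Seeing TC images has no evident route to change that fact, so only recall error within one exam remains. The endpoint is exploratory (3.2.3), and 10.3.3 plans no breast-order summary for it.
- Readers' repeat requests (6.2) are made blinded to mode (5.3.2).
- The primary endpoint comes from those readers, and force, thickness and dose come from the DICOM header.

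**The case against.** The strongest reply is that item 2 already tells the technologist to consider PAC alone, that Section 11.1.1 has forms filled in as the information arises, and that Section 6.1 does not bar an earlier source note. The repeat analysis is descriptive, no hypothesis is tested, and half of the endpoint's input comes from blinded readers. Earlier recording is also only a partial cure: the technologist would still know that TC imaging always follows, and a pause in mid-exam interrupts the workflow under study.

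Much of this limits the point without removing it. An instruction to set knowledge aside is weaker than asking before the knowledge exists. Section 11.1.1 is a general rule, whereas Section 6.1 gives these items a specific, later time; nothing requires a PAC answer before TC. The narrow reach and the partial nature of the cure both stand, and they are why the point is minor.

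A reader might go further and infer that the PAC workflow data do carry over from TC. The documents support only a possibility: two opposite mechanisms are plausible and neither is quantified. A reader might also extend the point to the intervention item, but that is a factual record. Nor can the gap be put at exactly four views against two, since that assumes a sequence that the available text does not settle.

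**Conclusion.** The point holds as a risk to the technologist component of one secondary endpoint, for PAC only. The hypothetical repeat judgement is always due after TC imaging of the same breast, from an unblinded technologist, and may be influenced by it in either direction and to an unknown degree. Each changed answer counts for 3.3 points overall and about 6.7 points in a breast-order subgroup, assuming 30 evaluable subjects split about evenly. The likely longer delay in the first-breast group could blur the subgroup summary of repeats; its size depends on the imaging sequence. The intervention item carries minor recall error only. No conclusion about the primary endpoint, the blinded reader requests or the DICOM-derived values is affected. This is a minor improvement, worth making because it is cheap and because the bias, if present, could not be repaired in analysis.

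**What to change.** In Section 6.1, have the PAC repeat item recorded and time-stamped after the last PAC view and before the first TC compression of that breast. For convenience, take the PAC intervention item at the same moment. Leave the TC repeat item and the DICOM items at the end of the exam. If the sequence in Figure 4 pairs PAC and TC within each view, the same principle means recording after each PAC view and before the matching TC compression. State in Section 6.1 how this timing fits with the general rule in Section 11.1.1, so that the two do not point to different times.

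The cost is a few tick boxes and a short pause between the PAC and TC acquisitions, with the subject waiting. No extra imaging, staff or subjects are needed, and the sample size is unchanged. The change does not remove the difference between a hypothetical PAC repeat and an actual TC repeat; the report should still say that the two proportions measure different things.

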2.7 Anticipated Risks and Benefits

The device under study has undergone risk assessment, in accordance with International Standards Organization (ISO) 14971:2012. Risks have been mitigated to levels as low as reasonably possible (ALARP) and are not expected to exceed risks associated with the routine clinical breast cancer screening procedures that the subject has been prescribed outside of the study. The operator’s manual highlights warnings, cautions, and potential conventional risks associated with the exam.

Breast imaging procedures will be conducted using post-market Senographe Pristina systems with post-market PAC installed. Breast imaging procedures will be conducted per the site’s standard of care, with the exception of the

investigational imaging, which will consist of unilateral two-view (craniocaudal [CC] and mediolateral oblique [MLO]) acquisitions using PAC during DBT imaging. There will be no repeat imaging administered using PAC.

No additional medications will be administered beyond those regularly required for the subject's medical care outside of this study, and regular medication should not be adversely impacted or delayed by study participation. Post-trial care and follow-up are not required by this study.

There is no expected benefit to study subjects participating in this research. The results of this study may benefit future patients by increasing knowledge about PAC with Senographe Pristina 3D.

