3.1.2 Secondary Objectives

The secondary objectives are:

- To evaluate the need for repeat image acquisition when using PAC and TC compression modes; and
- To evaluate acceptability of mammographic attributes for unilateral two-view breast images acquired using PAC and TC compression modes, per the *Guidance for Industry and FDA Staff - Class II Special Controls Guidance Document: Full-Field Digital Mammography System* (2012; hereafter referred to as the “Guidance”).

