3.2.2 Secondary Endpoints

The secondary endpoints are:

- Number of incidences per image set when the technologist and/or readers indicate a repeat acquisition for PAC and TC compression; and
- Acceptability of mammographic attributes, as defined in the *Guidance* and as described in Section 6.2 Image Attribute Review Data.

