5.3.2 Image attribute review

Following acquisition, study-specific 3D images will be de-identified, and the time stamp, compression force, and breast thickness will be removed from the DICOM header to ensure the readers are blinded to the compression mode used for each image set. The image sets will be randomized for presentation during the image attribute reviews.

The 3D PAC and TC compression image sets will be evaluated by two (2) MQSA-qualified readers, with a third reader to provide adjudication if disagreement is observed between the two (2) readers' evaluations of "overall clinical image quality" (i.e. item number 9 in Section 5.3.2 Image attribute review). Images will be displayed on site-provided mammography review workstations/systems per the previously defined randomization scheme. Each reader will evaluate each image set independently from other reader(s) and have the freedom to navigate between views, as he/she would do in clinical practice.

In addition to the images, the following case data will be available to the readers for each image set during image attribute review:

- Techniques (anode, filter, kVp, mAs, half-value layer)
- Estimated average glandular dose per view (mGy)

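### The technologist repeat item records a judgement for PAC but a performed act for TC, and the plan does not say which TC view is read after a repeat

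*Combined protocol and SAP*

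**What the plan says.** After each exam, Section 6.1 puts one repeat question to the technologist for each mode. For PAC it is "Considering PAC only, would you have repeated the image acquisition"; for TC it is "Considering the TC compression only, did you repeat image acquisition". Both are yes/no with the same four reasons.

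The PAC item is hypothetical because PAC repeats are barred. Section 2.7 says "There will be no repeat imaging administered using PAC" and Section 5.3.1 says "There shall be no repeat imaging administered using PAC mode". TC imaging follows standard of care (Synopsis, Procedures/Methods), and the TC item itself shows that repeats are foreseen.

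The secondary objective in Section 3.1.2 is "To evaluate the need for repeat image acquisition when using PAC and TC compression modes". The endpoint in Section 3.2.2 is "Number of incidences per image set when the technologist and/or readers indicate a repeat acquisition for PAC and TC compression". Section 10.3.3 summarises, by mode, the proportion of sets for which a repeat was indicated.

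On what is read, Section 5.3.1 states "There will be two (2) study-specific image sets of the breast of interest for each subject", one per mode, each made of a CC and an MLO view. Section 5.3.2 states "The 3D PAC and TC compression image sets will be evaluated by two (2) MQSA-qualified readers". Sections 5.3.1, 5.3.2, 6.2, 10.3.2, 10.3.3 and 10.4 do not say which acquisition enters the TC set when a TC view was repeated. Figure 4 is not shown in the text available, so a rule drawn there cannot be excluded. The reader repeat questions in Section 6.2 are worded identically for both modes.

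**The concern.** The study compares two modes, and two of its measurement rules differ by mode.

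- **Technologist item.** For PAC it captures a view that a repeat was needed. For TC it captures that a repeat was done. A TC view that the technologist thought should be repeated, but did not repeat, is recorded as no. The same opinion about a PAC view is recorded as yes.
- **View that is read.** The PAC set is always a first attempt. If the repeated TC view goes to the readers, the TC set may hold a second, corrected attempt. The separate acceptability proportions in Section 10.3.2 and the reader repeat answers would then compare unlike things.

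Section 10.1 states that no hypothesis is tested, so no error rate is at risk. What is at stake is the reading of a descriptive comparison that Section 3.1 intends as support for regulatory submissions.

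**Working it through.** **Inputs.** From Section 10.2: 30 subjects, one PAC set and one TC set each. The documents give no failure rate, repeat rate or share of indicated repeats performed, so every rate below is an assumption.

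**The plan's own precision figure, for scale.** Section 10.2 gives a 95% interval no wider than 13% at a proportion of 95%. The half-width without continuity correction is 1.96 × √(0.95 × 0.05 / 30) = 0.078. The interval runs from 0.872 to 1.000 after cutting at 100%, a width of 12.8%, which reproduces the figure. Section 10.3.2 plans a continuity correction, which adds 1/(2 × 30) = 0.0167. The half-width is then 9.5 points at 95% and, by the same formula, 0.1074 + 0.0167 = 12.4 points at 90%.

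**1. Technologist item.** Let p be the true need for a repeat, equal in both modes, and s the share of indicated TC repeats that are performed. PAC records p and TC records p·s, so PAC minus TC is p(1 − s).

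| p | s = 1 | s = 0.75 | s = 0.5 |
|---|---|---|---|
| 5% | 0 | +1.25 points (0.375 of 30) | +2.5 points (0.75 of 30) |
| 10% | 0 | +2.5 points (0.75 of 30) | +5 points (1.5 of 30) |

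This takes the hypothetical answer at face value. If technologists state a hypothetical need at h times the true rate, the gap becomes p(h − s). Its sign depends on h and s, and the documents inform neither.

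**2. Separate acceptability proportions.** Let q be the first-attempt failure rate, equal in both modes, and r the share of TC failures that are repeated, corrected and read. PAC acceptability is 1 − q and TC acceptability is 1 − q(1 − r), so PAC minus TC is −q·r.

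| q | r = 0 | r = 0.5 | r = 1 |
|---|---|---|---|
| 5% | 0 | −2.5 points (0.75 of 30) | −5 points (1.5 of 30) |
| 10% | 0 | −5 points (1.5 of 30) | −10 points (3 of 30) |

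If a repeat can itself fail at rate q, and r is only the share repeated, the gap is q·r·(1 − q). For r = 0.5 to 1 this is 2.4 to 4.75 points at q = 5% and 4.5 to 9.0 points at q = 10%. If the first TC view is read, the gap is zero.

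**3. Primary proportion (PAC equal to or better than TC).** A pair counts against PAC only when PAC is unacceptable and TC is acceptable. With independent failures the proportion is 1 − q[1 − q(1 − r)]. With all failures in the same subjects it is 1 − q·r.

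| q | Failures | r = 0 | r = 0.5 | r = 1 |
|---|---|---|---|---|
| 5% | independent | 95.25% | 95.125% | 95.0% |
| 5% | same subjects | 100% | 97.5% | 95.0% |
| 10% | independent | 91.0% | 90.5% | 90.0% |
| 10% | same subjects | 100% | 95.0% | 90.0% |

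Under independence the largest shift is 1.0 point, or 0.01 × 30 = 0.3 of one subject. The fall reaches 2.5 to 10 points only when failures coincide.

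**The case against.** The PAC question has to be hypothetical, and both questions concern the same decision. A technologist working to standard of care who judges a TC repeat necessary can perform it, so s may be 1 and the gap zero. No passage suggests otherwise. The endpoint also joins technologist and readers with and/or. If a set is flagged when any of them indicates a repeat, a first-attempt failure on which the technologist acts flags the set once in either mode, whichever TC view is read.

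On the view read, the comparator is the standard mode (Section 2.4), so a final standard-of-care set is a defensible choice. The value r = 1 is extreme: technologists would have to catch and correct every set that the readers would reject. Even then the gaps of 5 and 10 points lie inside the half-widths of 9.5 and 12.4 points for a single proportion. The shift from the view read goes against PAC, the mode that the submission is meant to support. Section 6.1 also records which subjects had a TC repeat, so they can be identified afterwards.

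Much of this stands, and it limits the point to an inexpensive improvement. Three things remain. The TC item cannot show a repeat that was indicated but not performed, although the objective concerns need. Section 10.3.3 does not say how technologist and reader indications are combined, so the and/or reading is only one possibility. And although either TC view could be justified, the text names neither; a first view that has not been kept cannot be read later.

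**Conclusion.** The technologist part of the repeat comparison sets a hypothetical judgement against a performed act. The resulting gap is zero if every indicated TC repeat is performed, and 1.25 to 5 points for assumed p of 5 to 10% and s of 0.75 to 0.5. Its true direction cannot be known from the documents.

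In addition, the text does not name the TC view to be read. If it is the repeated one, the separate acceptability proportions are biased against PAC by 0 to 5 points at q = 5% or 0 to 10 points at q = 10%. The reader repeat answers are affected in the same way. With no TC repeats this second issue disappears.

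A reader might infer more than this, and the documents do not support it:

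- *The primary result is compromised.* Under independence it moves by at most 0.3 of one subject in 30 over the range examined. A larger fall needs failures in the same subjects. That is possible, since both modes image the same breast, but nothing documents it.
- *Readers will be shown repeated TC views.* The text is silent, and Figure 4 is not available to settle it.
- *Each failure is tallied per rater and so weighs more heavily for PAC.* Section 10.3.3 analyses a proportion of sets, not a sum over raters.
- *The design favours PAC.* The shift from the view read runs against PAC, and the wording effect has no known sign.

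**What to change.** Before the first exam:

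1. **Section 6.1.** Ask the same question for both modes about the first acquisition: was a repeat indicated, and for what reason? Record whether a TC repeat was performed as a separate item.
2. **Section 10.3.3.** Report technologist-indicated and reader-indicated repeats separately, by mode.
3. **Section 5.3.2.** Name the TC view that is read, preferably the first completed acquisition of each view, to match PAC. If the final clinical view is read instead, report the acceptability and reader-repeat results also without the subjects whose TC view was repeated.

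The cost is a rewording and one extra CRF item, one reporting line and one sentence. Under the preferred option, first TC views must be kept and exported, and where a view was repeated the set read is not the final clinical set. No extra acquisition is needed, and nothing changes in when the site repeats a view.

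### The technologist's TC repeat item is not limited to the 3D images of the breast of interest, so repeats from outside the image set can count against TC only

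*Combined protocol and SAP*

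**What the plan says.** The first secondary endpoint (Section 3.2.2) is the "Number of incidences per image set when the technologist and/or readers indicate a repeat acquisition for PAC and TC compression". Section 10.3.3 analyses it as follows: "The proportion of image sets indicated for repeated image acquisition when using PAC mode or TC mode will be summarized".

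The unit is the image set. Section 5.3.1 defines it for the breast of interest: "Image sets will consist of CC and MLO views obtained using PAC and CC and MLO views obtained using TC compression". The Synopsis (sample size) gives the target as 60 evaluable 3D sets, 30 per mode, and Section 5.3.2 sends only 3D images to the readers.

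The technologist's part comes from two items in Section 6.1, each answered once when the exam is complete. Item 2, for PAC: "Considering PAC only, would you have repeated the image acquisition". Item 3, for TC: "Considering the TC compression only, did you repeat image acquisition". Each continues "If yes, please select the option below that best describes the reasoning", offering positioning, compression, motion or other. Neither item records the view, the breast, or whether a 3D or a 2D image was at fault.

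The imaging differs between modes. Section 2.7 describes the investigational imaging as unilateral two-view "acquisitions using PAC during DBT imaging". TC imaging follows site practice (Synopsis, Procedures/Methods). Under Section 5.3.1 that practice is combo mode with the 3D acquisition first, and the site "does not decompress between 3D and 2D imaging for a given view". The other breast is imaged under standard of care, for which Section 2.4 names TC as the standard compression mode.

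**The concern.** The form and the endpoint do not have the same scope. The PAC item is closed by design: PAC produces only the two DBT views of the breast of interest, so a yes can refer to nothing else. The TC item is open. A technologist who repeats a TC view because the woman moved during the 2D exposure, or who repeats a view of the other breast, answers yes truthfully. Neither event concerns the 3D image set, and PAC has no opportunity to generate either one.

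Once entered, such an answer cannot be separated from a 3D repeat, because no recorded field distinguishes them and Section 10.3.3 has no rule to exclude it. The endpoint wording joins technologist and readers with and/or, so a technologist's yes can flag a set by itself.

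At stake is the interpretability of the first secondary endpoint, in a study meant to support regulatory submissions for PAC with the 3D option (Section 3.1). Part of any TC excess in repeats could reflect what was counted rather than the compression mode.

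**Working it through.** **Plan's own figure.** 30 subjects × 2 modes = 60 image sets, 30 per mode, as stated. The endpoint's denominators are therefore equal. The documents give no repeat rate and no count of acquisitions at risk.

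**Acquisitions at risk per subject, by reading of item 3**

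| Reading of item 3 | PAC exposures | TC exposures | PAC compressions | TC compressions |
|---|---|---|---|---|
| 3D, breast of interest | 2 | 2 | 2 | 2 |
| 3D and 2D, breast of interest | 2 | 4 | 2 | 2 |
| 3D and 2D, both breasts | 2 | 8 | 2 | 4 |

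Only the first row matches the image-set definition. The item as worded permits all three.

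**Model for the second row.** Let c be the probability per compression of a positioning or compression fault, and m the probability per exposure of a motion fault. Assume that faults are independent, equally likely in both modes, and that m is the same for 3D and 2D exposures.

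- PAC: P(flag) = 1 − [(1−c)(1−m)]²
- TC with 2D counted: P(flag) = 1 − [(1−c)(1−m)²]²

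For small probabilities the ratio is about (c+2m)/(c+m) = 1 + motion share, hence 1 to 2.

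**Example, assumed c + m = 3% per view**

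- No motion (c = 0.03, m = 0): both modes 1 − 0.97² = 0.0591. Ratio 1.00, excess 0.
- One third motion (c = 0.02, m = 0.01): PAC 0.0587, TC 0.0774. Ratio 1.32, excess 30 × 0.0187 = 0.56 flags.
- One half motion (c = m = 0.015): PAC 1 − 0.985⁴ = 0.0587, TC 1 − 0.985⁶ = 0.0867. Ratio 1.48, excess 0.84.
- All motion (c = 0, m = 0.03): PAC 0.0591, TC 1 − 0.97⁴ = 0.1147. Ratio 1.94, excess 1.67.

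**Range over assumed c + m** (ratio; extra TC flags in 30)

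| c + m per view | no motion | 1/3 motion | 1/2 motion | all motion |
|---|---|---|---|---|
| 1% | 1.00; 0 | 1.33; 0.20 | 1.49; 0.29 | 1.98; 0.59 |
| 3% | 1.00; 0 | 1.32; 0.56 | 1.48; 0.84 | 1.94; 1.67 |
| 5% | 1.00; 0 | 1.31; 0.90 | 1.46; 1.34 | 1.90; 2.64 |
| 10% | 1.00; 0 | 1.29; 1.60 | 1.43; 2.38 | 1.81; 4.62 |

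**Third row.** If technologists also counted the other breast, then at 3% per view the ratio would be 1.94 with no motion repeats (0.1147/0.0591) and 3.66 with all motion ([1 − 0.97⁸]/0.0591 = 0.2163/0.0591). With the other breast included, the ratio no longer falls to 1.0 when motion is absent, because the compressions are then 2 against 4.

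**After restriction to the first row**, both modes have 2 exposures and 2 compressions, and the ratio is 1.0 for any c and m.

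**The case against.** The strongest reply is that the endpoint is already defined per image set and image sets are 3D, so item 3 should be read that way. This is right about the intended target: no passage says that the item covers the whole combo exam. But technologists answer the form, and the form does not carry the limit. The same document states a 3D restriction for the exploratory endpoints (Section 3.2.3) and asks readers which view they would repeat (Section 6.2, item 10b). It does neither for the technologist's repeat item. The eCRF itself is not in the documents, and completion guidelines are only optional (Section 11.1.1), so the gap may be closed elsewhere, but nothing shown closes it.

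A reader might infer that TC has twice the chances of a repeat and that the endpoint is therefore tilted toward PAC. The documents do not support either step. Twice is right for exposures in the breast of interest, but the 3D and 2D images share one compression per view. Positioning and compression, two of the three named reasons, are thus at risk largely once per view in either mode, and a doubling requires every repeat to be for motion. Nor is a net tilt shown. The readers see only 3D sets and answer the same questions for both modes, so their part is symmetric. The technologist's PAC item is hypothetical while the TC item records what was done, and the direction of that difference is unknown.

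It also stands that no hypothesis is tested (Section 10.1) and that repeats have no success criterion, so no error rate or primary result is affected. Figure 4, which shows the sequence, is not available; the sequence used here rests on the text.

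**Conclusion.** The concern holds as a mismatch between form and endpoint. Item 3 can count 2D-prompted and other-breast repeats against TC, PAC has no matching opportunity, and the recorded data cannot separate them afterwards. Taken alone, the mechanism has zero effect or favours PAC.

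For the breast of interest, the TC-to-PAC ratio with no true difference lies between 1.0 and about 2.0. At an assumed 3% per view, this is 0 to about 1.7 extra TC flags in 30, against about 1.8 expected for PAC (30 × 0.059). The size rests on assumed repeat rates and motion shares, on independent faults, and on equal motion risk for 3D and 2D exposures. Counting the other breast would make it larger.

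The net direction for the complete endpoint is not established. The consequence is confined to a descriptive secondary endpoint, but correcting the form costs little and should be done before data collection.

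**What to change.** In Section 6.1, item 3 and the matching eCRF page, record for each TC repeat: the breast (breast of interest or other), the view (CC or MLO), and whether the 3D image, the 2D image or both prompted it.

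In Sections 3.2.2 and 10.3.3, add one sentence: the TC repeat endpoint counts only repeats prompted by the 3D acquisition of the breast of interest, including those prompted by 3D and 2D together. List repeats prompted by 2D alone, or by the other breast, separately as workflow data.

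The cost is a few extra CRF fields and possibly a slightly lower TC repeat count, with no added imaging. The change does not resolve the hypothetical-versus-actual wording of items 2 and 3, which remains a separate limit on comparing the two modes.
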